6.3. Efficacy Analyses

Efficacy analyses will be performed based on data of efficacy analysis set.

- 1) Best overall response [Complete response (CR), Partial response (PR), Stable disease (SD), Progressive disease (PD), Not evaluable (NE)] will be presented in frequency and percentage.
- 2) Objective response rate (ORR) will be presented in frequency and percentage.

Objective response rate (ORR)

$$= \frac{\text{Number of subjects who achieves a best overall response of CR or PR}}{\text{Number of subjects in the efficacy analysis set}}$$

Statistical Analysis Plan for rPMS

- 3) Kaplan-Meier curve for time-to-event endpoints will be generated and presented quartiles with 95% CI, event rates and censor rates. Date of death is date of resolution of serious adverse event in which the category of seriousness is 'Results in death'. In case subjects do not have an event, censor of time-to-event is performed at the date of final follow-up.
 - Progression-free survival (PFS)
 - Time to progression (TTP)
- 4) Objective response rate (ORR) by demographic and other baseline characteristics
 - Objective response rate and 95% CI will be presented by categorical variables of demographic and other baseline characteristics.
 - To identify statistically significant difference in objective response rate by categorical variables of demographic and other baseline characteristics, Chi-square test (χ^2 test) or Fisher's exact test (if the expected frequency for each cell under 5 is more than 20%) will be performed.
- 5) Analysis of factors that affect the efficacy
 - In the re-examination report, logistic regression or multivariate analysis will be performed and an odds ratio with 95% CI and p-value will be presented to identify the factors that affect objective response rate in demographic and other baseline characteristics.

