### 3.5.4.9. Safety

#### 3.5.4.9.1. Adverse Event

Every observed and reported adverse event, regardless of the causal relationship with the study drug, must be recorded on an adverse event section in case report forms. The query pattern of experience of adverse event to the subjects is as follow;

Patients who are prescribed with INLYTA® for the first time during the study period: “Have you had any health problem since last visit?”

Patients who are already on INLYTA® at the time of enrollment: all safety information will be collected from medical chart since the date of treatment initiation.

For adverse events repeating before and after administrating the study drug, record the date adverse event was first experienced and the date adverse event resolved. Background information on INLYTA® can be obtained from the current version of the local product document, which is the single reference safety document (SRSD) for information relating to INLYTA®.

Check either ‘yes’ or ‘no’ in adverse event section. If ‘yes’, record in detail.

- Adverse events: Record the name of adverse event. If possible, specify diagnosis, not individual symptoms. Record the name according to National Cancer Institute Common Terminology Criteria for Adverse Events (CTCAE) Version 5.0.
- Date of onset: Record the date of onset. Record approximate date if an actual date is unknown.
- Date of resolution: Record the date of resolution. Record approximate date if an actual date is unknown.
- Severity: Severity evaluation of adverse event must be done according to the NCI CTC grade.
  - The physician will use the following definitions of severity in accordance with the National Cancer Institute Common Terminology Criteria for Adverse Events (CTCAE) Version 5.0 to describe the maximum intensity of the adverse event:

Grade	Definition
Grade 1	Mild; asymptomatic or mild symptoms; clinical or diagnostic observations only; intervention not indicated.
Grade 2	Moderate; minimal, local or noninvasive intervention indicated; limiting age-appropriate instrumental ADL*.
Grade 3	Severe or medically significant but not immediately life-threatening; hospitalization or prolongation of hospitalization indicated; disabling; limiting self care ADL**.
Grade 4	Life-threatening consequences; urgent intervention indicated.
Grade 5	Death related to AE.

Activities of Daily Living (ADL)

\*Instrumental ADL refer to preparing meals, shopping for groceries or clothes, using the telephone, managing money, etc.

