\*\*Self care ADL refer to bathing, dressing and undressing, feeding self, using the toilet, taking medications, and not bedridden.

If the severity of an adverse event changed, the adverse event must be entered separately. Record stop date of previous severity and onset date of new severity – along with completion of all other items.

- Seriousness: Check either 'yes' or 'no'. If 'yes', record the appropriate number for the category of seriousness.

A serious adverse event is any untoward medical occurrence in a subject administered a medicinal or nutritional product (including pediatric formulas) at any dose that:

- (1) results in death;
- (2) is life-threatening;
- (3) requires inpatient hospitalization or prolongation of hospitalization;
- (4) results in persistent or significant disability/incapacity(substantial disruption of the ability to conduct normal life functions);
- (5) results in congenital anomaly/birth defect.

Progression of the malignancy under study (including signs and symptoms of progression) should not be reported as a serious adverse event unless the outcome is fatal within the safety reporting period. Hospitalization due to signs and symptoms of disease progression should not be reported as a serious adverse event. If the malignancy has a fatal outcome during the study or within the safety reporting period, then the event leading to death must be recorded as an adverse event and as a serious adverse event with severity Grade 5.

Lack of efficacy should be reported as an adverse event when it is associated with a serious adverse event.

Medical and scientific judgment is exercised in determining whether an event is an important medical event. An important medical event may not be immediately life-threatening and/or result in death or hospitalization. However, if it is determined that the event may jeopardize the subject or may require intervention to prevent one of the other outcomes listed in the definition above, the important medical event should be reported as serious.

Examples of such events are intensive treatment in an emergency room or at home for allergic bronchospasm; blood dyscrasias or convulsions that do not result in hospitalization; or development of drug dependency or drug abuse.

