Additionally, any suspected transmission via a Pfizer product of an infectious agent, pathogenic or non-pathogenic, is considered serious. The event may be suspected from clinical symptoms or laboratory findings indicating an infection in a subject exposed to a Pfizer product. The terms “suspected transmission” and “transmission” are considered synonymous. These cases are considered unexpected and handled as serious expedited cases by PV personnel. Such cases are also considered for reporting as product defects, if appropriate.

In case of serious adverse event, Drug Safety Unit in Pfizer Pharmaceuticals Korea is to be notified promptly by the physician.

Check the following at the end of the study or after the resolution of adverse event.

- Outcome: The evaluation of outcome will include: Record the date of recovery in case of ‘Recovered’ or ‘Recovered with sequelae’.
  - Recovered
  - Recovered with sequelae
  - Recovering
  - Not recovered
  - Unknown

- Causality of adverse event to the study drug: The causal relationship of adverse event to the study drug must be allocated by the physician according to the following criteria.

(1) Certain

- It follows a reasonable time sequence from administration of the drug (before and after the study medication).
- It could not be explained by other drugs, chemical substance or accompanying diseases.
- It has clinically reasonable reaction on cessation of the drug.
- It has pharmacological or phenomenological reaction to re-administration of the drug, where necessary.

(2) Probable/likely

- It follows a reasonable time sequence from administration of the drug (before and after the study medication).
- It could not be explained by other drugs, chemical substance or accompanying diseases.
- It has clinically reasonable reaction on cessation of the drug.

(No information on re-administration)

(3) Possible

- It follows a reasonable time sequence from administration of the drug.
- It could also be explained by other drugs, chemical substance or accompanying diseases.
- It lacks information or has unclear information on discontinuation of the drug.

(4) Unlikely

- It is not likely to have a reasonable causal relationship from administration of the drug. Rather, it seems to be temporary.
- It could also be reasonably explained by other drugs, chemical substances or latent diseases.

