4.2. Efficacy Endpoints

- Tumor response based on RECIST 1.1
- Objective Response Rate (ORR)

ORR will be defined as the number of subjects who achieve a best overall response of complete response (CR) or partial response (PR), divided by the total number of subjects in efficacy analysis set.

- Progression-free survival (PFS)

PFS is defined as the time from first dose of study medication to first documentation of objective tumor progression, or to death due to any cause, whichever occurs first.

- Time to progression (TTP)

TTP is defined as the time from the first dose of study medication to objective tumor progression excluding death.

5. General Consideration

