5.2. Handling of Missing and Incomplete data

5.2.1. Handling of Missing data

If data are missing or if a subject decides to discontinue from the study, there will be no imputation applied except as specified in section 5.2.2. The impact of missing data will be evaluated as appropriate.

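### PFS takes the date of death only from the resolution date of a fatal SAE, a field never defined as the date of death, so some deaths may be censored or misdated

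*SAP*

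**What the plan says.** SAP 4.2 runs PFS from first dose to "first documentation of objective tumor progression, or to death due to any cause, whichever occurs first". TTP has the same start but leaves deaths out, so deaths are all that separates the two endpoints.

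SAP 6.3, item 3, then fixes the source of the death date: "Date of death is date of resolution of serious adverse event in which the category of seriousness is 'Results in death". It names no other source. Subjects without an event are censored at final follow-up.

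On missing values, SAP 5.2.1 says "there will be no imputation applied except as specified in section 5.2.2". Section 5.2.2 covers only the date of initial diagnosis and the end date of ongoing study drug.

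The field that the SAP relies on is in Protocol 3.5.4.9.1, among the items for every adverse event: "Date of resolution: Record the date of resolution. Record approximate date if an actual date is unknown". Further on, the outcome item in that section has its own date instruction, "Record the date of recovery in case of" the two recovered categories. The remaining outcomes are recovering, not recovered and unknown. SAP 6.2 repeats the same five categories.

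**The concern.** A site completing the form for a fatal event finds no fatal outcome to tick. The closest option is not recovered, which by its meaning describes an event that has not resolved. The outcome item wants no date for that option, and nothing tells the site to put the date of death in the resolution field. A blank there is an understandable entry, and the SAP then has no date for the death.

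At stake is the death component of PFS. Protocol 3.1 mandates no visits, so scans follow routine practice, and Appendix 4 recognises patients who stop treatment for general deterioration without objective progression. For such patients death may be the only PFS event. Censoring them is informative, because they leave the risk set by dying, and it lengthens the estimated PFS. A blank date may also pass unnoticed, appearing as one more censored subject and one fewer in the death row of Table 27.

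**Working it through.** The plan gives no PFS estimate, event count or expected share of deaths, so there is no figure of its own to reproduce. The check is first textual, then a scaling calculation.

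**Following a death through the forms**

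1. Is the death recorded? During observation, in general yes. Protocol 3.5.4.9.1 requires all adverse events regardless of causality, and death is the first seriousness category.
2. Is a date requested? Yes. The resolution date is asked for every event, with no recovery condition and with approximate dates allowed. Only the separate recovery date under outcome is conditional.
3. Is that date defined as the date of death? No instruction in the protocol says so.
4. Is there another source? The data items in Protocol 3.5.4.2 to 3.5.4.10 include neither a date of death nor survival status.
5. Is there a rule for a blank? No. SAP 5.2.1 says only that the impact of missing data will be evaluated as appropriate.

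The chain is weak at steps 3 to 5. A blank leaves no event date, and the only disposition that the SAP gives a subject without an event is censoring at final follow-up. A loosely approximated date misplaces the death, in either direction.

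**Size if deaths are lost**

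Let λ be the total PFS event hazard, assumed constant; q the share of first PFS events that are deaths without documented progression; and m the share of those deaths that are lost to censoring.

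- True median = ln 2 / λ.
- Hazard seen by the analysis = λ(1 − qm).
- Ratio of apparent to true median = 1 / (1 − qm).

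Example: q = 0.20 and m = 0.50 give 1 / (1 − 0.10) = 1 / 0.90 = 1.111, a rise of 11.1%.

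| q | m | Formula | Rise in median | Simulated rise |
|---|---|---|---|---|
| 5% | 50% | 1/0.975 | 2.6% | 2.6% |
| 5% | 100% | 1/0.95 | 5.3% | 5.2% |
| 10% | 50% | 1/0.95 | 5.3% | 5.2% |
| 10% | 100% | 1/0.90 | 11.1% | 11.0% |
| 20% | 50% | 1/0.90 | 11.1% | 11.0% |
| 20% | 100% | 1/0.80 | 25.0% | 25.1% |
| 30% | 50% | 1/0.85 | 17.6% | 18.1% |
| 30% | 100% | 1/0.70 | 42.9% | 42.5% |

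The last column comes from 2,000 simulated Kaplan-Meier analyses per row, with 100 subjects each, exponential PFS times and uniform censoring between 0.5 and 6 true medians. It agrees with the formula to within 0.5 percentage points. Neither q nor m has a source in the documents.

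**The case against.** The best defence is that the field exists and is requested for every event. A site can enter the date of death as the resolution date, and the rule then works as intended. The CRF is not among the documents, and Protocol 3.4 leaves variable detail to the SAP and CRF, so a CRF instruction or a death field cannot be ruled out. This removes any certainty of loss. It does not repair the SAP, which would not use a separate death field even if there were one.

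Several stronger readings are tempting, and the documents do not carry them:

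- *The protocol wants the date only on recovery.* A reader might infer this from the outcome item, but the general resolution item has no such condition.
- *Earlier records of the same event will supply a false date.* On a change of grade the protocol says "Record stop date of previous severity and onset date of new severity", so one fatal event can have two records. The wrong date enters only if a site also flags the superseded record as fatal, which nothing tells it to do. The SAP should still say which record counts.
- *Later cancer deaths go missing.* One sentence says that progression "should not be reported as a serious adverse event unless the outcome is fatal within the safety reporting period"; two sentences on, recording is required for a fatal outcome either in the study or in that period. The wording differs, but Protocol 5.1.2 runs the reporting period to the end of observation, so the two largely overlap. Later deaths fall mostly outside the limited follow-up that Protocol 3.5.3.2 sets for PFS, and deaths after documented progression do not alter PFS.
- *The five-year survival figure shows that the loss is large.* Overall mortality does not say how many deaths precede documented progression.

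**Conclusion.** The gap is real and moderate in weight. PFS includes death from any cause, while its only death date comes from a field that is not defined as the date of death, sits beside an outcome list with no fatal option, and has no fallback when blank. Followed as written, the plan may censor or misdate deaths that occur before documented progression. Lost deaths bias PFS upward towards TTP; the effect of a misdated death depends on which way the date is wrong.

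For q between 10% and 20%, the median rises by about 5% to 11% if half of the deaths are lost and by 11% to 25% if all are. These figures assume constant hazards and assumed values of q and m. A reader might infer that PFS will become TTP, but that requires every such death to be lost, which the documents do not show.

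The weight is limited because the study's objective is to monitor use and adverse events, Protocol 3.9.1.2 summarises efficacy descriptively, and no powered comparison rests on PFS.

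**What to change.** 1. In SAP 6.3, item 3, define date of death as an explicitly recorded date of death from any cause, taken from the chart or SAE report and independent of SAE status.
2. If that is absent, use the resolution (stop) date of the Grade 5 record. Do not use the date of an earlier-grade record of the same event. Do not use the Grade 5 onset date either: severity is graded at maximum intensity, so a fatal event entered as a single record may have begun well before death.
3. If both are blank, query the site before database lock rather than censor by default.
4. Add a fatal outcome with a date of death to the outcome list in Protocol 3.5.4.9.1, to SAP 6.2 and to Table 17.
5. Reconcile the two sentences on fatal progression in Protocol 3.5.4.9.1, which recur in 5.2.2.

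The cost is a few lines of SAP text, the matching protocol wording, one outcome category, one CRF field and some chart look-up for deaths already reported.

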## **3. RESEARCH METHODS**

### **3.1. Study design**

Observational, non-interventional drug and multi-center study in which subjects will be administered as part of routine practice at Korean health care centers by accredited physicians. At least 3000 subjects should be enrolled in this study based on the Article 6 of “Basic Standards for the Re-examination of New Medicines” notified by MFDS. However, with additional 3 years of study period, at least 100 subjects who are being treated with Inlyta within the approved indication will be studied for total of 9 years according to the review result by the MFDS per Pfizer’s request to adjust the number of subjects. The study can be performed in Korean health care centers where INLYTA® is prescribed for advanced renal cell carcinoma (aRCC) after failure of one prior systemic therapy which is the indication for INLYTA® and where post-marketing study is allowed by institutions.

To achieve the target sample size, the study is being conducted in prospective study design and retrospective study design.

Patients to whom INLYTA® is first administered or patients who are already on INLYTA® during the study period should be enrolled in the study. Observation should be done from treatment initiation of INLYTA® for at least 28 calendar days. There are no visits or activities mandated by this study and routine observation will be done during INLYTA® treatment.

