##### **3.5.3.2. Efficacy Endpoints**

- Tumor response based on RECIST 1.1
- ORR
- PFS within limited follow-up period
- TTP

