**3.5.4.8. Administrative Status for Study Drug**

INLYTA® is provided by the physician's prescription and Pfizer Korea will not provide drug for this study.

Record the following with regard to administrative status for the study drug.

- Duration of administration: Record the start date and stop date of the medicated drug (year / month / day). If the medication is being continued at the completion of the study, check the box next to 'ongoing'.
- A single dose: Record the dose (in mg) of study drug. In case of dose titration up or down, record each dose with the periods respectively.
- Daily dosing frequency: Record dosing frequency per day.
- Reason for dose adjustment: Record any remarks if applicable

Refer to LPD for posology and method of administration.

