#### **3.5.4.10. Efficacy Assessment**

The determination of antitumor efficacy will be based on objective tumor assessments made according to the Response Evaluation Criteria in Solid Tumors (RECIST) 1.1 of unidimensional evaluation. Progression-free survival (PFS) is defined as the time from first dose of study medication to first documentation of objective tumor progression, or to death due to any cause, whichever occurs first. And Time To Progression(TTP) is defined as the time to progression is one way to see how well a new treatment works. PFS will be assessed using the Kaplan-Meier method. Estimate of the PFS curves from the Kaplan-Meier method will be presented.

- Date of Tumor Assessment: Record the actual date that the scan was performed.
- Overall response: Check in **ONE** box indicating the overall tumor assessment based on RECIST Tumor Assessment Criteria.

Refer to [Appendix 4] for RECIST 1.1 Tumor Assessment Criteria.

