3.2. Efficacy Analysis Set

Efficacy analysis set will be included subjects to whom INLYTA® is administered INLYTA® at least once. Subjects who are excluded from the safety analysis set shall be excluded from the efficacy analysis set.

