5.2.2. Handling of Missing and Incomplete dates

Missing or incomplete dates will be handled by following rule:

	Missing	Imputation
Date of initial diagnosis	DD	01
	MM/DD	01/01
	YYYY/MM/DD	No imputation
End date of administration for study drug	'Ongoing'	Date of final follow-up

6. Statistical Analyses

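### PFS and TTP are censored at an undefined final follow-up date, so time without tumour assessments can count as progression-free

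*SAP*

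**What the plan says.** SAP 6.3 item 3 covers PFS and TTP with one rule: "In case subjects do not have an event, censor of time-to-event is performed at the date of final follow-up". The same item takes the date of death from the resolution date of a serious adverse event classed as fatal.

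The censoring date is not defined in the protocol or the SAP. The term appears once more, in SAP 5.2.2, where "Date of final follow-up" is the stand-in end date of dosing for subjects marked as ongoing. Protocol 3.5.4.8 describes that entry as follows: "If the medication is being continued at the completion of the study, check the box next to" the ongoing option. The scan has its own field in Protocol 3.5.4.10: "Date of Tumor Assessment: Record the actual date that the scan was performed". SAP 6.3 does not use it for censoring.

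SAP 4.2 defines PFS as the time from first dose to "first documentation of objective tumor progression, or to death due to any cause, whichever occurs first"; for TTP, death is not an event. Protocol 3.1 states: "There are no visits or activities mandated by this study and routine observation will be done during INLYTA® treatment". Protocol 3.5.3.2 lists "PFS within limited follow-up period" and gives no length. SAP 3.2 reads: "Efficacy analysis set will be included subjects to whom INLYTA® is administered INLYTA® at least once", apart from subjects excluded from the safety set. Table 26 of the SAP attachment has a row for subjects whose assessment was not done.

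**The concern.** An event-free time should end when the subject was last known to be event-free. For progression, that is the last tumour assessment. If censoring falls later, the subject stays in the risk set over a period in which progression could not have been recorded. Each such subject adds to the denominator but cannot contribute a progression, so the Kaplan-Meier curve falls too slowly. A subject who was never scanned is credited with the whole of follow-up.

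At stake are the PFS and TTP quartiles, event and censoring rates and curves in Tables 27 and 28 and Figures 1 and 2, each repeated by sub-group. Because the date is undefined, two programmers could also produce different tables from the same data.

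**Working it through.** **No plan figure to reproduce.** The documents give no expected PFS, scan interval, event count or follow-up length. The minimum of 100 subjects is a regulatory number.

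**Which date is meant.** Both the use in SAP 5.2.2 and the ongoing box in Protocol 3.5.4.8 concern a subject's status at the end of the study. The scan date has a separate field that the rule does not name. A general follow-up date is therefore the natural reading, though not a certain one. The CRF, to which Protocol 3.4 also refers for variable detail, was not available.

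**What can be observed in unscanned time.** For TTP, nothing. For PFS, only a death recorded as a fatal SAE.

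**Never-assessed subjects, by hand.** Assume median PFS of 6 months (exponential), a never-scanned share p = 0.10 followed for at least 12 months, and deaths making up a share d of the PFS hazard. Ignore scan delay.

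- Scanned subjects: S = 0.5^(12/6) = 0.25.
- Never-scanned subjects, for whom only death can be seen: 0.25^d.
- Present rule: S(12) = 0.9 × 0.25 + 0.1 × 0.25^d.
- d = 0: 0.225 + 0.100 = 0.325, which is 7.5 points too high.
- d = 0.25: 0.225 + 0.0707 = 0.296, which is 4.6 points too high.

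Simulation with scan delay gives 4.2 to 7.2 points above a complete scan schedule, and 5.1 to 7.2 above last-assessment censoring (never-scanned subjects censored at day 1). The latter difference is 0.0–0.1, 0.4–0.8 and 1.8–2.2 points if they are followed 1, 3 and 6 months. At 12 months it is 2.5–3.6 points if 5% are never scanned and 10.3–14.4 if 20% are. From 3 months on, the present rule is further from the complete schedule in 6 of 6 scenarios.

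**Subjects who stop being scanned, by simulation.** All inputs are assumed: median PFS 6 months; scans every 2 or 3 months ±25%; 20% or 40% stop scans between the first scan and month 12; d = 0, 0.15 or 0.25; final follow-up 28 days, 3 months or 6 months after the last scan. That gives 12 scenarios per gap, with 150,000 subjects each. The benchmark is the curve if everyone had kept to the scan schedule. Figures are percentage points at 12 months.

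| Gap | PFS: present minus last-assessment | TTP: same | PFS: present minus benchmark | PFS: last-assessment minus benchmark | Present rule closer to benchmark |
|---|---|---|---|---|---|
| 28 days | 0.6 to 1.8 | 0.7 to 3.4 | −0.9 to 0.0 | −2.7 to −0.6 | 9–12 of 12 |
| 3 months | 1.9 to 4.9 | 2.2 to 6.4 | +0.7 to +3.2 | −2.9 to −0.8 | 6 of 12 |
| 6 months | 3.4 to 9.1 | 4.1 to 10.2 | +2.0 to +7.1 | −3.4 to −0.8 | 0 of 12 |

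The range 9–12 reflects two ways of dating follow-up for subjects who die. The two rules are equally far from the benchmark at a gap of 1.0 to 1.6 scan intervals.

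On median PFS, present minus last-assessment is about 0.1–0.4, 0.2–1.3 and 0.4–1.7 months at the three gaps.

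**Different assumptions.** With no deaths, medians of 4 to 12 months, follow-up running 3 to 6 months after imaging stops and 0 to 20% never scanned, the difference at 12 months is about 6 to 20 points. The inputs drive the size.

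**Sampling noise at N = 100.** For 12-month PFS of 0.25, √(0.25 × 0.75/100) = 4.3 points before censoring, and about 5 with it. For the median, the standard error is 6/(ln 2 × √100) = 0.87 months.

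**The case against.** The best defence is that no long gap is documented. Protocol 3.1 ties routine observation to treatment. Subjects marked as ongoing are still on drug and under routine care. Protocol 5.1.3 prolongs follow-up only for drug-related events. Appendix 4 asks for effort to document progression after treatment stops, which would shorten the gap. The one relevant number is the 28-day safety minimum in Protocol 5.1.2, and at 28 days the present rule is the closer one. The CRF might define the date. Tables 27 and 28 report quartiles, not 12-month PFS. Protocol 3.9.1.2 makes efficacy descriptive, and SAP 6.3 plans no test on PFS or TTP. Last-assessment censoring has a downward bias of its own.

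Most of this stands, and it limits the claim. A reader might infer that the reported PFS is certain to be inflated, or that all unscanned time is event-free for PFS. The documents support neither: the gap is unknown, and deaths recorded as fatal SAEs still count. A reader might also infer that last-assessment censoring is always the more accurate rule. At gaps shorter than about one scan interval it is not.

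The objection does not remove the missing definition or the treatment of never-assessed subjects. Those subjects are in the efficacy set whatever the usual gap, and the SAP has no rule for them. The 28 days is a safety minimum and does not bound the time since the last scan. The table row for assessments not done shows that the SAP allows for such subjects, though not how many there will be.

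**Conclusion.** The point holds in a limited form and should be fixed. The censoring date is undefined, and on its natural reading unscanned time counts as progression-free: fully for TTP, and for PFS except for deaths recorded as fatal SAEs. Upward bias is clear for never-assessed subjects followed about 3 months or more and for gaps beyond about one scan interval. For shorter gaps the present rule is no worse, and if the term means the last assessment there is no bias.

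The size cannot be derived from the documents. The figures of about 2 to 9 points of 12-month PFS (gaps of 3 to 6 months) and 5 to 7 points (10% never scanned, followed 12 months) rest on an assumed 6-month median and assumed scan and drop-out patterns. Effects at short gaps are below sampling noise at 100 subjects. Confidence is high that the definition is missing and in the direction of the effect when the gap is long, but not that a long gap will occur. No formal decision depends on these estimates.

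**What to change.** In SAP 6.3 item 3:

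- Define the final follow-up date, and say what makes a tumour assessment evaluable.
- Censor event-free subjects, for PFS and TTP, at the last evaluable tumour assessment. Censor never-assessed subjects without a recorded death at day 1.
- For TTP, censor deaths without progression at the last assessment.
- State how PFS deaths after missed scans are handled.
- Keep censoring at final follow-up as a sensitivity analysis.
- With Tables 27 and 28, report the number never assessed and, among censored subjects, the time from last assessment to final follow-up. Readers can then see whether the gap exceeds one scan interval.

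No new data are needed, because scan dates are already recorded. The cost is SAP wording, summary lines and the sensitivity outputs: two tables and two figures for the total and each of two sub-groups, so up to 4 × 3 = 12. Reported PFS and TTP will be somewhat shorter. In the assumed scan-stopping scenarios, last-assessment censoring puts 12-month PFS about 0.6 to 3.4 points below a complete schedule, more so when deaths follow missed scans. The sensitivity analysis makes that trade-off visible.
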